13.2.1 Causality Assessment

Causality Assessment – A determination of the relationship between an adverse event and the test article, study treatment, or study procedure. The test article, study treatment or study procedure relationship for each adverse event shall be determined by the Investigator using these explanations:

- Not Related- An adverse event that is not related to the use of the test article, study treatment or study procedures.

- **Doubtful** – An adverse event for which an alternative explanation is more likely, e.g. concomitant treatment, concomitant disease(s), or the relationship of time suggests that a causal relationship is unlikely.
- **Possible** – An adverse event that might be due to the use of the test article, or to the study treatment or study procedures. An alternative explanation, e.g. concomitant treatment, concomitant disease(s), is inconclusive. The relationship in time is reasonable. Therefore, the causal relationship cannot be excluded.
- **Probable** – An adverse event that might be due to the use of the test article. The relationship in time is suggestive (e.g. confirmed by de-challenge). An alternative explanation is less likely, e.g. concomitant treatment or concomitant disease(s).
- **Very Likely** – An adverse event that is listed as a possible adverse effect (device) or adverse reaction (drug) and cannot be reasonably explained by an alternative explanation, e.g. concomitant treatment or concomitant disease(s). The relationship in time is very suggestive, e.g. it is confirmed by de-challenge and re-challenge.

13.2.2 Severity Assessment

Severity Assessment – A qualitative assessment of the degree of intensity of an adverse event as determined by the Investigator or reported to him/her by the subject. The assessment of severity is made irrespective of test article, study treatment or study procedure relationship or seriousness of the event and should be evaluated according to the following scale:

- **Mild** – Event is noticeable to the subject, but is easily tolerated and does not interfere with the subject’s daily activities
- **Moderate** – Event is bothersome, possibly requiring additional therapy, and may interfere with the subject’s daily activities
- **Severe** – Event is intolerable, necessitates additional therapy or alteration of therapy and interferes with the subject’s daily activities

13.3. Documentation and Follow-Up of Adverse Events

The recording and documenting of adverse events (ocular and non-ocular) begins when the subjects are exposed to the test article, study treatment or study procedure. Adverse events reported before the use of test article, start of study treatment, or study procedures will be recorded as medical history. However, if the condition deteriorates at any time during the study it will be recorded and reported as an AE. Untoward medical events reported after the subject’s exit from the study will be recorded as adverse events at the discretion of the Investigator.

Upon finding an adverse event, the Principal Investigator will document the condition in the subject record and in the eCRFs. He/she will complete the Adverse Event /eCRF.

Complete descriptions of all adverse events must be available in the subject record. All Adverse Events including local and systemic reactions not meeting the criteria for “serious adverse events” shall be captured on the appropriate case report form or electronic data system. All adverse events occurring while the subject is enrolled in the study must be documented appropriately regardless of relationship.

It is the Investigator's responsibility to maintain documentation of each reported adverse event. All adverse events will be followed in accordance with applicable licensing requirements. Such documentation will include the following:

- Adverse event (diagnosis not symptom)
- Drawings or photographs (where appropriate) that detail the finding (e.g., size, location, and depth, etc.)
- Date the clinical site was notified
- Date and time of onset
- Date and time of resolution
- Adverse event classification, severity, and relationship to test articles, as applicable
- Treatment regimen instituted, including concomitant medications prescribed, in accordance with applicable licensing requirements
- Any referral to another health care provider if needed
- Outcome, ocular damage (if any)
- Likely etiology
- Best corrected visual acuity at the discovery of the event and upon conclusion of the event

In addition, if an infiltrate(s) is present, he/she will complete the Corneal Infiltrate Assessment /eCRF. Where necessary, a culture of the corneal lesion will be collected to determine if the infection is microbial in nature. If cultures are collected, the date of culture collection and laboratory utilized will be recorded.

Changes in the severity of an AE shall be documented to allow an assessment of the duration of the event at each level of intensity to be performed. Adverse events characterized as intermittent require documentation of the onset and duration of each episode. Changes in the assessment of relationship to the Test Article shall also be clearly documented.

Subjects who present with an adverse event shall be followed by the Investigator, within licensure, until all signs and symptoms have returned to pre-treatment status, stabilized, or been satisfactorily resolved. If further treatment beyond licensure is required, the patient will be referred to the appropriate health care provider. The Investigator will use his/her clinical judgment as to whether or not a subject reporting with an adverse event will continue in the study. If a subject is discontinued from the study, it will be the responsibility of the Investigator to record the reason for discontinuation. The Investigator will also document the adverse event appropriately and complete the Adverse Event /eCRF. Any subjects with ongoing adverse events related to the test article, study treatment or study procedures, as of the final study visit date should be followed to resolution of the adverse event or until referral to an appropriate health care provider, as recommended by the Investigator.

13.4. Reporting Adverse Events

The Investigator will notify the Sponsor of an adverse event by e-mail, facsimile, or telephone as soon as possible and no later than 24 hours from discovery for any serious /significant adverse events, and 2 days from discovery for any non-significant adverse event.

In addition, a written report will be submitted by the Principal Investigator to the IEC/IRB according to their requirements (Section 13.4.2). The report will comment whether or not the adverse event was considered to be related to the test article, study treatment or study procedures.

13.4.1 Reporting Adverse Events to Sponsor

Serious/Significant Adverse Events

The Investigator will inform the sponsor of all serious/significant adverse events occurring during the study period as soon as possible by e-mail, fax, or telephone, but no later than 24 hours following discovery of the event. The Investigator is obligated to pursue and obtain information requested by the Sponsor in addition to that information reported on the eCRF. All subjects experiencing a serious/significant adverse event must be followed up and all outcomes must be reported.

When medically necessary, the Investigator may break the randomization code to determine the identity of the treatment that the subject received. The Sponsor and study monitor should be notified prior to unmasking the test articles.

In the event of a serious/significant adverse event, the Investigator must:

- Notify the Sponsor immediately
- Obtain and maintain in the subject's records all pertinent medical information and medical judgment for colleagues who assisted in the treatment and follow-up of the subject
- Provide the Sponsor with a complete case history which includes a statement as to whether the event was or was not related to the use of the test article
- Notify the IEC/IRB as required by the IEC/IRB reporting procedure according to national regulations

Unanticipated (Serious) Adverse Device Effect (UADE)

In the event of an Unanticipated (Serious) Adverse Device Effect (UADE), the Investigator will submit a report of the UADE to the Sponsor and IEC/IRB as soon as possible, but no later than 24 hours after the Investigator first learns of the effect. This report is in addition to the immediate notification mentioned above.

The Sponsor must conduct an evaluation of the UADE and must report the results of the evaluation to FDA, the IEC/IRB and participating Investigators within 10 working days after the Sponsor first receives notification of the effect.

Non-Serious Adverse Events

All non-serious adverse events, including non-serious adverse device effects, will be reported to the sponsor by the Investigator no later than 2 days from discovery.

13.4.2 Reporting Adverse Events to the Responsible IEC/IRB and Health Authorities

Adverse events that meet the IEC/IRB requirements for reporting must be reported within the IEC/IRB's written guidelines. Each clinical site will refer to and follow any guidelines set

forth by their Approving IEC/IRB. Each clinical site will refer to and follow any guidelines set forth by their local governing Health Authorities.

The Sponsor will report applicable Adverse Events to the local health authorities according to the written guidelines, including reporting timelines.

13.5. Event of Special Interest

None

13.6. Reporting of Pregnancy

Subjects reporting pregnancy (by self-report) during the study will be discontinued after the event is recorded as an Adverse Event. Once discontinued, pregnant participants and their fetuses will not be monitored for study related purposes. At the Investigator's discretion, the study participant may be followed by the Investigator through delivery. However, this data will not be collected as part of the clinical study database. Pregnant participants are not discontinued from contact lens or solution related studies for safety concerns, but due to general concerns relating to pregnancy and contact lens use. Specifically, pregnant women are discontinued due to fluctuations in refractive error and/or visual acuity that occur secondary to systemic hormonal changes, and not due to unforeseen health risks to the mother or fetus.

14. STATISTICAL METHODS

14.1. General Considerations

All data summaries and statistical analyses will be performed using the SAS software Version 9.4 (SAS Institute, Cary, NC). Throughout the analysis of data, the results for each subject/eye will be used when available for summarization and statistical analysis. Unscheduled visits will be summarized separately and will be excluded from the statistical analysis.

Summary tables (Descriptive statistics and/or frequency tables) will be provided for all baseline variables, efficacy variables and safety variables as appropriate. Continuous variables will be summarized with descriptive statistics (n, mean, standard deviation (SD), median, minimum and maximum). Frequency count and percentage of subjects or eyes within each category will be provided for categorical data.

Summaries will be presented by study lens type and will be performed separately by completion status. All analyses will be conducted on per-protocol population (see section 14.3).

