4.15	Modifications	
If the subjects vision is unacceptable for at least one distance or the Investigator determines that the visual acuity or over-refraction are not acceptable then a lens modification must be made.
 
Up to two attempts at modification are permitted if necessary, to achieve an acceptable distance and near binocular performance for the subject, and to enable them to wear that particular lens type.
 
Follow the appropriate fitting guide allowing for at least 10 minutes of settling time between each lens modification attempted. If modifications are required steps 4.8 to 4.14 will be repeated for each modification.
	Appendix G or H Fitting Guides
4.16	PRO Post-Fit Questionnaire	The subject will evaluate the vision characteristics, comfort characteristics, handling characteristics, and visual symptoms of their study lenses using the PRO questionnaire.	
4.17	Exit Distance and Near Visual Acuity	
Distance and near Snellen visual acuity will be measured for each eye with the study contact lenses in place.
 
For near measures use the ETDRS 2000 Series Chart 1 or 2. The acuity will be recorded to the nearest letter OD, OS and OU.
 
Note: The distance visual acuity must be at least 20/30 OU for the lenses to be dispensed.
	██████████
4.18	Dispensing Criteria	
The lenses will be dispensed for 2-4 days.
 
 • Distance Snellen acuity equal to or better than 20/30 OU • Subject must indicate that the vision is acceptable. 	

		
 • Subject must indicate that the comfort of the lenses is acceptable. • Lenses must have an acceptable general lens fit. 	

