8.2. Withdrawal/Discontinuation from the Study

A subject will be withdrawn from the study for any of the following reasons:

- Subject death during the study period
- Subject withdrawal of consent
- Subject not compliant to protocol
- Subject lost to follow-up
- Subject no longer meets eligibility criteria (e.g. the subject becomes pregnant)
- Subject develops significant or serious adverse events causing discontinuation of study lens wear
- Subjects who have experienced a Corneal Infiltrative Event (CIE)
- Investigator's clinical judgment regarding the subject safety reasons (that it is in the best interest of the subject to stop treatment)
- Subject not compliant with study lens wear schedule
- Subject not successfully dispensed due to lack of efficacy and safety including poor vision, poor comfort or unacceptable fit

For discontinued subjects, the Investigator will:

- Complete the current visit (scheduled or unscheduled)
- Complete the Final Evaluation, indicating the reason that the subject was discontinued from the study
- Record the spherocylindrical refraction with best corrected distance visual acuity
- Collect used test article(s) (worn or brought to the visit) from the subject and discard them, unless otherwise stated in Section 7.2
- Collect all unused test article(s) from the subject

An additional subject may be enrolled if a subject discontinues from the study prematurely.

In cases where a subject is lost to follow-up, every possible effort must be made to contact the subject and determine the reason for discontinuation/withdrawal. The measures taken to follow up must be documented including two written attempts and a certified letter (or equivalent) as the final attempt.

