14.3. Analysis Populations

Safety Population:

All subjects who were administered any test article excluding subjects who drop out prior to administering any test article. At least one observation should be recorded.

Per-Protocol Population:

All subjects who have successfully completed all visits and did not substantially deviate from the protocol as determined by the trial cohort review committee prior to database hard lock (Per-Protocol Population). Justification of excluding subjects with protocol deviations in the per-protocol population set will be documented in a memo to file.

Intent-to-Treat (ITT) Population:

All randomized subjects regardless of actual treatment and subsequent withdrawal from study or deviation from protocol. At least one observation should be recorded.

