14.5. Primary Analysis

Primary efficacy analysis:

Visual Performance:

Near and distance binocular, high luminance, high contrast visual performance on logMAR scale will be analyzed separately using a linear mixed model to test for the difference between the study lens systems. Each model will include the experimental design factors: sequence of lens wear, lens wearing period and lens type as fixed effects. Other baseline characteristics known of importance such as age, gender, and/or add power will be included as fixed covariates when appropriate. The covariance between residual errors from the same subject across lens wearing periods will be selected based on the finite-sample corrected Akaike's Information Criterion (Keselman et al. 1998). Covariance structures considered may include: Homogenous compound symmetry (CS) and Unstructured covariance structure (UN). The structure that returns the lowest Akaike Information Criteria Corrected (AICC) will be selected as the structure that best fit the data.

Comparisons will be carried out using 95% confidence intervals constructed of least squared means (LSM) from the linear mixed models. Statistical superiority will be concluded if the upper limit of the confidence intervals of the test lens is below +0.01 logMAR for distance and +0.17 for near.

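### All analyses are confined to per-protocol completers, although subjects are withdrawn for poor vision, comfort or fit and each lens is tested against a fixed threshold

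*Combined protocol and SAP*

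**What the plan says.** - **Analysis set.** Section 14.1: "All analyses will be conducted on per-protocol population (see section 14.3". Section 14.3 defines that set as "All subjects who have successfully completed all visits and did not substantially deviate from the protocol". Section 8.1 makes anyone withdrawn under 8.2 a non-completer.
- **Other populations.** Section 14.3 also defines ITT ("All randomized subjects regardless of actual treatment and subsequent withdrawal from study or deviation from protocol") and a Safety Population. No analysis is assigned to either.
- **Withdrawal.** One reason in 8.2 is "Subject not successfully dispensed due to lack of efficacy and safety including poor vision, poor comfort or unacceptable fit". Sections 5.2 and 8.2 allow discontinued subjects to be replaced.
- **Dispensing.** The criteria in 7.2 at Visits 1, 2, 4 and 5 include "Distance Snellen acuity equal to or better than 20/30 OU" and "Subject must indicate that the vision is acceptable", with acceptable comfort and fit. Before that, "Up to two attempts at modification are permitted if necessary, to achieve an acceptable distance and near binocular performance for the subject".
- **Decision rule.** Section 14.5: "Statistical superiority will be concluded if the upper limit of the confidence intervals of the test lens is below +0.01 logMAR for distance"; the near threshold is +0.17. In 14.6 the lower CLUE limit must exceed 32.
- **Missing data.** Section 14.9 expects dropout to be a main cause of missing data, says past trials do not show it to be systematic, and plans multiple imputation as a sensitivity analysis if dropout exceeds 15%. It names no population.

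**The concern.** The endpoints are binocular acuity and quality of vision, and the rules that remove subjects name poor vision. A subject who cannot be dispensed either lens leaves the analysis of both. What remains is a group that succeeded with both lenses, and its mean is compared with a constant. A within-subject comparison of lenses would cancel much of such selection; a one-sample test does not.

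A conclusion of superiority would then describe successful wearers rather than everyone fitted, and section 14.2 says the data will be used to design future trials. The programmer also has no instruction on which set the 14.9 imputation uses, and collected period 1 endpoints are left out of the inference.

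**Working it through.** **1. The plan's own figures.** Section 14.2 gives about 80 enrolled and at least 60 completing, with no power calculation, so there is no power figure to reproduce. Implied attrition is 1 - 60/80 = 25%. This is an upper figure, since the 80 may include screen failures. The 15% trigger would be passed at 13 of 80 (12/80 = 15.0%; 13/80 = 16.3%).

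**2. Sections 14.1 and 14.9 together.** All analyses use completers. Completers contain no dropouts by definition. The dropout imputation therefore has nothing to act on, apart from sporadic missing items in completers. Both sections cannot be followed as written.

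**3. False-success rate.** A 95% interval compared with a fixed bound gives 2.5% in the success direction. Assumptions, none from the documents:
- each subject has a propensity to fail on each lens, bivariate normal with between-lens correlation 0.3 or 0.7;
- a subject is lost if either propensity exceeds a cut set to give the total loss;
- endpoint = r × propensity + √(1 - r²) × noise, where r is the correlation of the endpoint with the propensity to fail on that lens;
- 60 completers, true mean exactly on the threshold, t-interval in place of the model interval, 200,000 simulations per cell.

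Ranges cover the two between-lens correlations:

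| Total loss | r = 0 | r = 0.1 | r = 0.25 | r = 0.5 |
|---|---|---|---|---|
| 5% | 2.5% | 2.9% | 3.5-3.8% | 4.8-5.6% |
| 15% | 2.5% | 3.4-3.7% | 5.7-6.9% | 12-16% |
| 25% | 2.5% | 4.2-4.8% | 8.6-11% | 23-33% |

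A second model (80 randomized, within-subject correlation 0.6, withdrawal before each period's endpoint visit) gave no inflation at zero correlation. It gave 9.0% and 17.8% at 15% loss, and 14.3% and 33.3% at 25% loss, for withdrawal-endpoint correlations 0.3 and 0.5. Direction and order of size agree. The 17.8% lies above the table's range, so the ranges are illustrations and not bounds.

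**4. Shift in CLUE points.** Shift = 20 × k × r, with SD 20 from section 2.2 and k from the first model, for r = 0.25 to 0.5:
- 5% loss, k = 0.077-0.096: 0.4 to 1.0 points
- 15% loss, k = 0.197-0.244: 1.0 to 2.4 points
- 25% loss, k = 0.308-0.377: 1.5 to 3.8 points

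The documents give no logMAR SD.

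**5. The distance gate.** 20/30 is log10(30/20) = 0.176 logMAR, which is 0.176 - 0.01 = 0.166 worse than the distance threshold. Suppose the mean of 80 fitted subjects is on the threshold and q are withdrawn at that level or worse. The completer mean then falls by at least q × 0.166/(80 - q): 0.004, 0.009 or 0.018 logMAR for q = 2, 4 or 8. This treats Snellen acuity at dispensing as equal to the ETDRS endpoint; the values of q are assumed. There is no near-acuity gate, only the subject's acceptance of vision.

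**6. Visit 3 values left out.** In the first model, 40-47%, 35-45% and 32-42% of lost subjects have a Visit 3 endpoint at 5, 15 and 25% loss. With 60 completing, the numbers lost are 60/0.95 - 60 = 3.2, 60/0.85 - 60 = 10.6 and 60/0.75 - 60 = 20. That makes about 1-2, 4-5 and 6-8 values omitted.

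**7. What ITT alone recovers.** Using every available value by maximum likelihood removes 7-21% of the shift in the first model. For example, at 25% loss and r = 0.5, CLUE falls from 3.1 to 2.8 or from 3.8 to 3.2-3.4 points. In the second model it removes more: at 25% loss the bias falls from 0.115 to 0.081 SD (30%) at correlation 0.3 and from 0.189 to 0.138 SD (27%) at 0.5. It cannot remove the rest, because a subject who fails on the first lens has no endpoint at all.

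**The case against.** The strongest case for the plan has four parts.

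1. This is a pilot with exploratory hypotheses (14.4) and no power basis. Section 2.2 defines the endpoints after 6-8 days on an optimized lens, so performance among successfully fitted wearers is a legitimate question. This lowers the consequence. However, 14.5 and 14.6 still declare superiority, and nothing in the objectives limits the claim to successful wearers.
2. Section 14.9 is naturally read as applying to ITT, and 14.1 plans summaries by completion status, so Visit 3 values of non-completers could still be shown. ITT may well have been intended, but the literal wording of 14.1 excludes it. Descriptive summaries can coexist with 14.1, but they do not bring those values into the models.
3. The loss rate and both correlations are assumed, and the only statement on mechanism (14.9) points to no systematic dropout. The point about size stands. The remark on past trials does not, however, cover withdrawal rules that name poor vision.
4. The rates assume a true mean on the threshold. Far from it, selection hardly alters the decision. For CLUE with n = 60 and SD 20, the standard error is 20/√60 = 2.58. A true mean of 44 lies (44 - 32)/2.58 = 4.65 standard errors above 32, so success is nearly certain without any selection. This also stands: the decision is sensitive only near the threshold, although the estimate is shifted wherever the mean lies.

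**Conclusion.** The concern holds. Two parts follow from the text alone: the dropout imputation has no dropouts to work on in the set that 14.1 prescribes, and valid Visit 3 endpoints are left out of the inferential models when period 2 is not completed. The bias is conditional. It is zero if withdrawal is unrelated to the endpoint, and otherwise it favours superiority for both lenses. Its size cannot be established from the documents; the figures above rest on the stated loss rates, correlations and a true mean on the threshold. Above 15% dropout the 14.9 analysis would be triggered, but as a sensitivity analysis it would not change the primary decision. Given the pilot status this should be fixed, but it does not undermine the study.

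**What to change.** Replace the last sentence of 14.1 so that:

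1. the primary and secondary mixed models use the ITT population of 14.3 with every available Visit 3 and Visit 6 value, including single-period data;
2. the per-protocol analysis is a sensitivity analysis;
3. the 14.9 multiple imputation is run on ITT, optionally with a pre-stated range of adverse shifts for subjects withdrawn for vision, comfort or fit (assumed values, for example 0, 0.05 and 0.10 logMAR, and 0, 5 and 10 CLUE points);
4. adverse event and corneal staining summaries use the Safety Population, which otherwise has no assigned use;
5. the number and proportion of subjects who could not be dispensed each lens are reported beside its least squares mean.

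Items 3 and 5 are needed because item 1 recovers only part of the shift. No withdrawal or dispensing rule changes.

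The cost is SAP wording and a few extra tables, with no added subjects, visits or procedures. Estimates may be slightly less favourable. Selection is reduced and made visible, but not removed.

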8. SUBJECTS COMPLETION/WITHDRAWAL

8.1. Completion Criteria

Subjects are considered to have completed the study if they:

- provided informed consent;
- they are eligible;
- have not withdrawn/discontinued for any reason described in Section 8.2;
- Complete all study visits

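### Section 14.1 sends all analyses to the per-protocol set with no exception for safety, and the Safety Population defined in 14.3 is assigned to no table

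*Combined protocol and SAP*

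**What the plan says.** Section 14.1 (General Considerations) says that summary tables "will be provided for all baseline variables, efficacy variables and safety variables as appropriate". It continues: "Summaries will be presented by study lens type and will be performed separately by completion status". The next sentence, the last of the section, reads: "All analyses will be conducted on per-protocol population (see section 14.3". No exception is made for safety.

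Section 14.3 (Analysis Populations) defines three sets. The per-protocol set is "All subjects who have successfully completed all visits and did not substantially deviate from the protocol". The Safety Population is "All subjects who were administered any test article excluding subjects who drop out prior to administering any test article", with at least one observation recorded. The third is an intent-to-treat set. Neither the Safety Population nor the intent-to-treat set is mentioned again in Section 14.

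Section 8.2 lists the reasons for withdrawal. Two concern safety directly: "Subject develops significant or serious adverse events causing discontinuation of study lens wear" and "Subjects who have experienced a Corneal Infiltrative Event (CIE". Under Section 8.1, completers are those who "have not withdrawn/discontinued for any reason described in Section 8.2".

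Section 2.2 places the average corneal staining grade among the other endpoints, to be summarised, and names no population for it.

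**The concern.** A safety table should count everyone exposed to the lens. A completers-only set leaves out the subjects most likely to have had a troublesome event, because such an event is itself a reason for not completing. Here the only sentence in Section 14 that assigns a population points to that set, and the population built for safety is left unused. A programmer who follows 14.1 to the letter would produce adverse event and corneal staining tables without the subjects withdrawn for safety reasons, and those tables would understate lens-related harm.

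The design adds to the loss. In a 2x2 crossover, a subject withdrawn in the second period also leaves the per-protocol set for the first, so the safety data on the lens that caused no trouble go too. Section 14.2 says the data will feed the design of later trials, so an understated event rate could carry forward.

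**Working it through.** The plan states no figure on this point that could be reproduced. The sample size in 14.2 is not based on power. The check is therefore mainly of the text, with simple arithmetic for scale.

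**Can a subject withdrawn for an adverse event be in the per-protocol set?**

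1. Section 8.2 withdraws a subject with a corneal infiltrative event, or with a significant or serious adverse event that stops lens wear.
2. Section 8.1 does not count a subject withdrawn for any 8.2 reason as a completer.
3. Section 14.3 requires successful completion of all visits for the per-protocol set.
4. The per-protocol count of such subjects is therefore 0, taking completion in 14.3 in the sense of 8.1.

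**Do the last two sentences of 14.1 fit together?** This depends on what analyses means.

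- *Reading A: analyses covers everything, tables included.* The safety tables are then per-protocol. The split by completion status cannot be made, because the set holds no non-completers, so the two sentences conflict.
- *Reading B: analyses means only the mixed models of 14.5 and 14.6.* Safety is then descriptive and split by completion status, so non-completers appear and the conflict goes away. What is still missing is a table by lens over all exposed subjects. Separate tables for completers and non-completers do not state that rate, and no population is named for either. Findings at unscheduled visits, for which 7.3 lists an adverse event as a possible reason, are likewise summarised apart with no population named.

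**Scale.** Inputs from 14.2: about 80 enrolled and at least 60 completing.

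- Implied non-completion: (80 − 60)/80 = 20/80 = 25%. Check: 60/(1 − 0.25) = 80.
- The share outside the per-protocol set is larger if some of the 60 are excluded for deviations.

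The documents give neither the number exposed nor an adverse event rate. As an illustration, assume exactly 60 in the per-protocol set and k exposed subjects withdrawn for an adverse event. The number exposed then lies between 60 + k (the other non-completers never wore a lens) and 80 (all enrolled did):

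| k (assumed) | k/80 | k/(60 + k) | Per-protocol |
|---|---|---|---|
| 1 | 1.3% | 1/61 = 1.6% | 0/60 |
| 3 | 3.8% | 3/63 = 4.8% | 0/60 |
| 5 | 6.3% | 5/65 = 7.7% | 0/60 |
| 10 | 12.5% | 10/70 = 14.3% | 0/60 |

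The one-sided 95% upper bound for 0 of 60 is 1 − 0.05^(1/60) = 0.0487, or 4.9%. It says nothing about the withdrawn subjects. With k = 5, the proportion among the exposed is above that bound at either end of the range.

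**The case against.** The strongest reply is Reading B. Section 14.1 treats data summaries and statistical analyses as two things: it opens by naming both, and it lets unscheduled visits into the former while keeping them out of the latter. No inferential safety analysis is planned, and corneal staining is only to be summarised. Section 14.9 also plans multiple imputation for dropout above a threshold, which would have no dropouts to work on in a completers-only set. So the authors may not have meant the sentence literally, and the name and definition of the Safety Population make its purpose plain.

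Much of this stands. A reader might infer that every subject withdrawn for an adverse event is removed from the safety summaries by definition. The documents do not support that, because the split by completion status presupposes that non-completers are tabulated. Three further inferences go too far:

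- *That a quarter of exposed subjects are lost.* The figure of 80 counts enrolled subjects. Consent, baseline eligibility checks and lens insertion follow one another at Visit 1, and no exposed count is given.
- *That everyone who reacts badly to a lens is deleted.* Section 13.1 describes non-significant events as usually not requiring the lens to be stopped, and 13.3 leaves continuation after an event to the investigator's judgment. Such subjects can complete and stay in the per-protocol set.
- *That the event data are lost.* Section 13.3 requires every event during enrolment to be documented, and 13.4 sets reporting times to the sponsor.

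The reply does not remove the defect. Recording and expedited reporting do not set the population or denominator of a table. Reading B still gives no table over all exposed subjects, and nothing in Section 14 tells the programmer to choose it over Reading A.

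**Conclusion.** The point holds as a fault of assignment and consistency. The one sentence in Section 14 that names an analysis set sends all analyses to completers with no safety exception, and the Safety Population is used nowhere. On the literal reading, subjects withdrawn for a corneal infiltrative event or a lens-stopping adverse event are absent from the safety results, and two adjacent sentences conflict. On the narrower reading they are tabulated, but no summary by lens over all exposed subjects is specified.

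The size is about 20 of 80 enrolled (25%) outside the per-protocol set, taking the 14.2 numbers at face value, and more if completers are excluded for deviations. How many of these were exposed, or left because of an event, cannot be told from the documents.

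This should be fixed before database lock. It is not critical: the study is a pilot of marketed lenses, its hypotheses are exploratory, and none of them concerns safety.

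**What to change.** Replace the last sentence of Section 14.1 with:

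> Adverse events, biomicroscopy/corneal staining and ocular symptoms will be summarised on the Safety Population by lens worn at onset or assessment, overall and by completion status. The efficacy analyses in 14.5 and 14.6 will be conducted on the per-protocol population.

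The second sentence is needed because 14.5 and 14.6 name no population themselves. Deleting the present sentence without it would leave the primary and secondary models with no analysis set. The split by completion status becomes workable, since the Safety Population contains non-completers. The table specification should also say where an event with onset in the washout is counted, because no study lens is worn then.

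The cost is two sentences in place of one and a different population flag in the safety tables. No new data are needed, and the efficacy analyses do not change.
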